# 3.3 Rationale for dose/regimen, route of administration and duration of treatment

Phase 2 results for AMG 334 in EM patients are available for the doses of 7 mg and 21 mg (both of which have proven to be ineffective compared to placebo) and 70 mg, which has been shown to be effective. The PK of AMG 334 at 70 mg SC were similar for healthy Japanese and white subjects (ratio of geometric means [ie, Japanese/white] for Cmax, AUClast, and AUCinf = 1.02, 1.12, and 1.12, respectively). PK-exposure response modelling suggests that with higher doses, a potential additional benefit in terms of efficacy might be observed. The safety profile of AMG 334 has been investigated up to 280 mg in healthy volunteers in Phase 1 without a difference in safety profile. For these reasons, an additional dose of 140 mg was introduced into the CM Phase 2b trial as well as one of the Phase 3 trials for EM.

Results from the CM Phase 2b trial (Study 20120295) showed statistically significant and comparable results in both dose groups across the majority of endpoints, subgroups and timepoints. In the recently completed 20120296 trial in EM that included both 70 mg and 140 mg AMG 334, consistently higher treatment effects were observed with 140 mg and are considered clinically meaningful across different endpoints in the full population. This was also observed consistently across patient subgroups, suggesting additional efficacy for 140 mg in patients with episodic migraine in general.

The safety and tolerability profile of AMG 334 is comparable across both 70 mg and 140 mg. The only potentially dose-related adverse event observed in the trials completed to date has been constipation, which was observed in 4.3%/3.4% of patients with 140 mg in CM/EM compared to 0%/1.6% of patients with 70 mg in CM/EM. The cases of constipation were usually mild, transient and not clinically relevant.

Both the route of administration (subcutaneous injection) and the investigation of the 70 mg and 140 mg doses of AMG 334 are in line with the phase 2/3 trials and support the "bridging" approach of this trial to the broader AMG 334 development program. The 3-month study duration is endorsed by IHS guidelines as a sufficient duration to assess efficacy in prophylactic migraine treatment clinical trials.

## 3.4 Rationale for choice of comparator

The choice of a specific therapy for a migraine headache prophylactic often takes into account individual circumstances, comorbidities and patient preferences. Patients are currently being treated by a variety of drug classes that were originally developed for other indications, but were repurposed for migraine prophylaxis. Some drugs have been formally approved for migraine prophylaxis in many countries; the most common approved drugs are propranolol, metoprolol, topiramate and flunarizine. In some countries, additional choices exist that are only approved and/or available on a national level. Other drugs, while not formally approved, are considered acceptable alternatives and are recommended within national treatment guidelines. Examples with evidence for migraine headache prophylaxis include other drug classes such as antidepressants (mainly amitriptyline and venlafaxine), ACE/ARBs (mainly candesartan and lisinopril) and valproate/divalproex. All of those drugs are occasionally used as migraine prophylactics, but the use is off-label and rests on the individual clinical responsibility of the prescribing physician after an adequate individual benefit-risk assessment.

All of these therapies, regardless if approved or off-label, are commonly associated either with variable migraine efficacy and/or substantial tolerability issues that often lead to treatment discontinuation. The standard of care also varies significantly across different geographies and treatment decisions, particularly in patients that have already failed the standard first line therapies are often made on a case-by-case basis without general consensus on treatment guidelines. Because of the variability of standard of care across different geographies and the potential for functional unblinding due to typical adverse events with any active comparator, placebo was selected as the comparator. The short duration (12 weeks) of placebo treatment, in conjunction with the allowed use of acute migraine treatment, justifies the use of placebo in this study as also suggested in the IHS guidelines (Tfelt-Hansen 2012). All patients continue to receive best supportive care in form of acute abortive medications and other non-pharmacological interventions as appropriate.

### 3.5 **Purpose and timing of interim analyses/design adaptations**

A blinded interim assessment is planned after about 50% of subjects have completed their DBTP, including early withdrawals, to provide additional information on the variance of the primary endpoint in this trial. The purpose of this blinded interim analysis is to account for potential higher variability in new countries and sites and possibly modify the initially planned sample size as outlined in Section 9.7.

#### 3.6 Risks and benefits

Key risks and benefits are briefly summarized below. For further information, please refer to the current Investigator Brochure.

As of 08-May-2017, the safety of AMG 334 in migraine prophylaxis was assessed from integrated safety analyses of 2537 migraine patients exposed to at least one dose of AMG 334, with a cumulative exposure of 2310.3 subject-years (SY). Overall, the safety and tolerability profile of AMG 334 was similar between the 140 mg and 70 mg doses and also comparable to placebo. Adverse drug reactions include injection site reactions, constipation, muscle spasms, and pruritus. The majority were mild or moderate in severity and rarely led to treatment discontinuation. To date, no important risk has been identified for AMG 334.

Overall, to date, there is no evidence from nonclinical and clinical data of risk of cardiovascular effects. On the theoretical basis of the mechanism of action of AMG 334, CGRP receptor blockade may reduce compensatory vasodilation, particularly under ischemic conditions. Therefore, cardiovascular effects continue to be monitored, and patients with pre-existing cardiovascular disease will be excluded from participation.

All biologicals, including fully human proteins, have the potential to induce immunogenicity leading to the development of specific anti-drug antibodies. So far, the development of anti-AMG 334 antibodies has only been observed with low incidence and was not associated with specific adverse events or a clinically relevant reduction in AMG 334 plasma levels. Patients in clinical studies will continue to be monitored for the development of anti-AMG 334 antibodies and associated clinical sequelae.

Plasma levels of CGRP increase with advancement of pregnancy up to the time of delivery, followed by a sharp decline at term and postpartum in rats and humans. Endogenous CGRP may play an important role in maintaining normal fetoplacental development, fetal survival, and vascular adaptation during pregnancy. Women who are breastfeeding, pregnant, or planning to become pregnant are excluded from study participation, as well as patients who are unwilling to comply with the protocol-specified contraception requirements. All women of child bearing potential will be screened for pregnancy at each study visit.

An external data monitoring committee was established to review the AMG 334 safety data for Phase 2b and Phase 3a studies, and based on these data, recommended continuation of the program. The need for a data monitoring committee (DMC) for this study was assessed, and deemed not necessary because the safety profile of AMG 334 has already been well-characterized from 4 double-blind, placebo-controlled trials in over 2500 patients, and the ability to establish the DMC and meetings is limited due to the anticipated short patient recruitment duration and the double-blind duration of the study (12 weeks). The risk to patients in this trial will be minimized by compliance with the eligibility criteria, close clinical monitoring, and use of rescue medications.

Initial benefits for AMG 334 as a migraine prophylactic have been demonstrated in a Phase 2b trial (Amgen Study 20120178), in which 70 mg was established as the minimally effective dose in EM (Sun et al 2016) with a significant placebo-corrected reduction of 1.1 monthly migraine days compared to baseline, as well as positive results on most secondary endpoints, including 50% responder rate, reduction of acute medication use and overall headache hours.

Initial long-term data are available from the open-label extension of the Phase 2b EM Study 20120178. In the latest interim data cut (28-Jan-2016), efficacy data from 383 patients were included who received at least one dose of AMG 334 in the open-label treatment phase and had  $\geq$  4 migraine days at baseline of the double-blind treatment period. Sustained efficacy was observed in the open-label extension through Week 64 for reduction in monthly migraine days, responder rates and PRO endpoints (Ashina et al 2016).

Three additional Phase 2/3 studies, including 2 studies in EM, have been completed with AMG 334, which have established 70 mg and 140 mg as being effective and safe in patients with EM or CM, with a favorable benefit/risk profile. Positive treatment effects in general were observed in a robust way across typical migraine endpoints such as change in mean monthly migraine days, > 50% (and higher) responder rates, change in migraine-specific medication use and functional improvement by established PRO scales. Results were in general highly statistically significant and clinically meaningful. As described in Section 3.3, in episodic migraine a dose-dependent increase in efficacy has been observed for the 140 mg dose. Retention rates observed in clinical trials were very high (~95% with active treatment after 3 months and ~90% after 6 months with only minimal discontinuations attributed to

adverse events). This feature is important, as discontinuation rates are high for current migraine prophylaxis treatments, with the main drivers of discontinuation being either lack of efficacy or tolerability issues (Blumenfeld et al 2013). As such, there is a high unmet need for a therapy that is well-tolerated, has sustained response rates and excellent compliance.

Overall, given the characteristics of AMG 334 and the large experience in clinical trials, the overall benefit-risk assessment is supportive.

# 4 Population

The study population will consist of male and female patients, ages 18 to 65, with a documented history of episodic migraine as outlined in the inclusion criteria.

The goal is to randomize approximately 880 patients in approximately 100 centers worldwide. Assuming a 40% screening failure rate, approximately 1467 patients will be screened.

### 4.1 Inclusion criteria

Patients eligible for inclusion in this study must fulfill **all** of the following criteria:

- 1. Written informed consent must be obtained before any assessment is performed.
- 2. Adults  $\geq$  18 to  $\leq$  65 years of age upon entry into screening
- History of migraine (with or without aura) for ≥ 12 months prior to screening according to the IHS Classification ICHD-3 (Headache Classification Committee of the International Headache Society, 2013) based on medical records and/or patient self-report
- 4. Migraine frequency 4 to 14 migraine days per month on average across the 3 months prior to screening (refer to Section 6.4.1 for the definition of migraine day)
- 5. Headache (ie, migraine and non-migraine headache) frequency < 15 headache days per month on average across the 3 months prior to screening (refer to Section 6.6.1 for the definition of headache day)
- 6. Migraine frequency 4 to 14 migraine days during the baseline period based on the eDiary calculations
- 7. Headache frequency < 15 headache days during the baseline period based on the eDiary calculations
- 8. Demonstrated at least 80% compliance with the eDiary (for example, completing eDiary items for at least 23 out of 28 days during the baseline period)

## 4.2 Exclusion criteria

Patients fulfilling any of the following criteria are not eligible for inclusion in this study:

- 1. Older than 50 years of age at migraine onset
- 2. History of cluster headache or hemiplegic migraine headache
- 3. Unable to differentiate migraine from other headaches
- 4. No therapeutic response with > 2 of the following 7 medication categories for prophylactic treatment of migraine after an adequate therapeutic trial. These medication categories are:
  - Category 1: Divalproex sodium, sodium valproate

- Category 2: Topiramate
- Category 3: Beta blockers (for example: atenolol, bisoprolol, metoprolol, nadolol, nebivolol, pindolol, propranolol, timolol)
- Category 4: Tricyclic antidepressants (for example: amitriptyline, nortriptyline, protriptyline)
- Category 5: Serotonin-norepinephrine reuptake inhibitors (for example: venlafaxine, desvenlafaxine, duloxetine, milnacipran)
- Category 6: Flunarizine, verapamil
- Category 7: Lisinopril, candesartan

No therapeutic response is defined as no reduction in headache frequency, duration, or severity after administration of the medication for at least 6 weeks at the generally accepted therapeutic dose(s) based on the investigator's assessment.

The following scenarios do not constitute lack of therapeutic response:

- Lack of sustained response to a medication
- Failure to tolerate a therapeutic dose
- 5. Used a prohibited medication, device, or procedure within 2 months prior to the start of or during the baseline period, or during the DBTP (Refer to Section 5.5.8 for the list of these excluded treatments)
- 6. Received botulinum toxin in the head and/or neck region within 4 months prior to the start of the baseline period or during the baseline period
- 7. Taken the following for any indication in any month during the 2 months prior to the start of the baseline period:
  - Ergotamines or triptans on  $\geq 10$  days per month, or
  - Simple analgesics (nonsteroidal anti-inflammatory drugs [NSAIDs], acetaminophen) on  $\geq$  15 days per month, or
  - Opioid- or butalbital-containing analgesics on  $\geq$  4 days per month
- 8. Anticipated to require any excluded medication, device, or procedure during the study (Refer to Section 5.5.8 for the lists of these medications, devices, and procedures). Traditional medications and/or procedures are allowed if used at a stable dose/frequency for at least three months prior to randomization, and during the study
- 9. Active chronic pain syndromes (such as fibromyalgia and chronic pelvic pain)
- 10. History of major psychiatric disorder (such as schizophrenia and bipolar disorder), or current evidence of depression based on a Beck Depression Inventory (BDI)-II total score > 19 at screening. Subjects with anxiety disorder and/or major depressive disorder are permitted in the study if they are considered by the investigator to be stable and are taking no more than 1 medication for each disorder. Subjects must have been on a stable dose within the 3 months prior to the start of the baseline period.
- 11. History of seizure disorder or other significant neurological conditions other than migraine. Note: A single childhood febrile seizure is not exclusionary.
- 12. History of malignancy of any organ system (other than localized basal cell carcinoma of the skin or in situ cervical cancer), treated or untreated, within the past 5 years, regardless of whether there is evidence of local recurrence or metastases.

- 13. Human immunodeficiency virus (HIV) infection by history
- 14. Hepatic disease by history or total bilirubin ≥ 2.0 x upper limit of normal (ULN) or alanine transaminase (ALT) or aspartate aminotransferase (AST) ≥ 3.0 x ULN, as assessed by the central laboratory at initial screening
- 15. Myocardial infarction (MI), stroke, transient ischemic attack (TIA), unstable angina, or coronary artery bypass surgery or other revascularization procedure within 12 months prior to screening
- 16. History or evidence of any other unstable or clinically significant medical condition, that in the opinion of the investigator, would pose a risk to subject safety or interfere with the study evaluation, procedures or completion
- 17. Subject has any clinically significant vital sign, laboratory, or electrocardiogram (ECG) abnormality during screening that, in the opinion of the investigator, could pose a risk to subject safety or interfere with the study evaluation
- 18. Score "yes" on item 4 or item 5 of the Suicidal Ideation section of the Columbia Suicide Severity Rating Scale (C-SSRS), if this ideation occurred in the past 6 months, or "yes" on any item of the Suicidal Behavior section, except for the "Non-Suicidal Self-Injurious Behavior" (item also included in the Suicidal Behavior section), if this behavior occurred in the past 2 years.
- 19. Evidence of drug or alcohol abuse or dependence within 12 months prior to screening, based on medical records, patient self-report, or positive urine drug test performed during screening (with the exception of prescribed medications such as opioids or barbiturates)
- 20. Pregnant or nursing (lactating) women
- 21. Women of child-bearing potential, defined as all women physiologically capable of becoming pregnant, unless they are using basic methods of contraception during dosing of investigational drug. Basic contraception methods include:
  - Total abstinence (when this is in line with the preferred and usual lifestyle of the subject. Periodic abstinence (eg, calendar, ovulation, symptothermal, post-ovulation methods) and withdrawal are not acceptable methods of contraception
  - Female sterilization (have had surgical bilateral oophorectomy with or without hysterectomy), total hysterectomy or tubal ligation at least six weeks before taking investigational drug. In case of oophorectomy alone, only when the reproductive status of the woman has been confirmed by follow up hormone level assessment
  - Male sterilization (at least 6 m prior to screening). For female subjects on the study, the vasectomized male partner should be the sole partner for that subject
  - Barrier methods of contraception: Condom or Occlusive cap (diaphragm or cervical/vault caps). For UK: with spermicidal foam/gel/film/cream/vaginal suppository
  - Use of oral, (estrogen and progesterone), injected or implanted hormonal methods of contraception or other forms of hormonal contraception that have comparable efficacy (failure rate <1%), for example hormone vaginal ring or transdermal hormone contraception or placement of an intrauterine device (IUD) or intrauterine system (IUS)

In case of use of oral contraception women should have been stable on the same pill for a minimum of 3 months before taking investigational drug.

Women are considered post-menopausal and not of child bearing potential if they have had 12 months of natural (spontaneous) amenorrhea with an appropriate clinical profile (eg age appropriate, history of vasomotor symptoms) or have had surgical bilateral oophorectomy (with or without hysterectomy), total hysterectomy or tubal ligation at least six weeks ago. In the case of oophorectomy alone, only when the reproductive status of the woman has been confirmed by follow up hormone level assessment is she considered not of child bearing potential.

- 22. Use of other investigational drugs within 5 half-lives of enrollment, or until the expected pharmacodynamic effect has returned to baseline, whichever is longer.
- 23. History of hypersensitivity to any of the study drugs or its excipients or to drugs of similar chemical classes.
- 24. Previously randomized into an AMG 334 study
- 25. Unlikely to be able to complete all protocol required study visits or procedures, and/or to comply with all required study procedures (eg, independent completion of electronic diary [eDiary] items) to the best of the subject's and investigator's knowledge. No additional exclusions may be applied by the investigator, in order to ensure that the study population will be representative of all eligible patients.

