# 5.3 Treatment assignment and randomization

At Visit 110 (Day 1), all eligible patients/subjects will be randomized via Interactive Response Technology (IRT) to one of the treatment arms. The investigator or his/her delegate will contact the IRT after confirming that the patient fulfills all the inclusion/exclusion criteria. The IRT will assign a randomization number to the patient, which will be used to link the patient to a treatment arm and will specify a unique medication number for the first package of study drug to be dispensed to the patient. The randomization number will not be communicated to the caller.

The randomization numbers will be generated using the following procedure to ensure that treatment assignment is unbiased and concealed from patients/subjects and investigator staff. A patient randomization list will be produced by the IRT provider using a validated system that automates the random assignment of patient numbers to randomization numbers. These randomization numbers are linked to the different treatment arms, which in turn are linked to medication numbers. A separate medication list will be produced by or under the responsibility of Novartis Drug Supply Management using a validated system that automates the random assignment of medication numbers to packs containing the investigational drug(s).

Randomization will be stratified by prior prophylactic migraine treatment failure according to the planned randomization ratio within each stratum. The randomization scheme for patients/subjects will be reviewed and approved by a member of the Randomization Group.

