#### Confidential

#### Novartis Clinical Trial Protocol (Version 00)

#### Page 35 Protocol No. CAMG334A2302

Period	Scree	ning			Treatm	nent		Follow-Up
Visit Name	Screening	Baseline	Treatment	Week 2 	Week 4	Week 8	End of Treatment	Follow-Up
Visit Numbers 	1	20	110	120	130	140	150 and TD/PSD	1999
Days	-42 to -28	-28 to -1	Day 1	14	28	56	84	168
Weeks	-6 to -4	-4 to -1	1	2	4	8	12	24
Healthcare Resource Questionnaire					X 			
Headache Impact Test (HIT-6)			Х		Х	Х	Х	
	_				-			
Adverse Events9			Х	Х	Х	Х	Х	х
Serious Adverse Events 	Х	Х	Х	Х	Х	Х	Х	Х
Concomitant medications	Х	Х	Х	Х	Х	Х	X	Х
Concomitant therapies	Х	Х	Х	Х	Х	Х	Х	Х
Study completion information							Х	Х

 Visit structure given for internal programming purpose only

 Telephone visit.

 Height collected at screen visit only. Weight collected at screen, baseline, and End of Treatment Visit. Blood pressure, pulse and body temperature collected at every visit.

 Hepatitis testing consists of Hepatitis B Core Antibody (HepBcAb), Hepatitis B Surface antigen (HepBsAg), and Hepatitis C virus antibody. If the result for HepBcAb is positive and HepBsAg is negative, additional testing for Hepatitis B virus DNA by Polymerase Chain Reaction (PCR) is necessary. If both are positive, no additional testing is necessary.

 Patients will record headache and headache medication information daily, using the provided eDiary platform.

 To be completed by the patient after each headache.

 Completed daily via the eDiary.

 Adverse Events will be collected from the randomization (Visit 110) through the end of the Follow-Up Period (16 weeks after the last dose of study drug). Events occurring between screen and the first dose of investigational product should be captured as medical history, if warranted.

 SAEs will be collected after signing of the informed consent through the end of the Follow-Up Period (16 weeks after the last dose of study drug).

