## 8 Data review and database management

#### 8.1 Site monitoring

Before study initiation, at a site initiation visit or at an investigator's meeting, a Novartis representative will review the protocol and data capture requirements with the investigators and their staff. During the study, Novartis employs several methods of ensuring protocol and GCP compliance and the quality/integrity of the sites' data. The field monitor will visit the site to check the completeness of patient records, the accuracy of data capture / data entry, the adherence to the protocol and to Good Clinical Practice, the progress of enrollment, and to ensure that study treatment is being stored, dispensed, and accounted for according to specifications. Key study personnel must be available to assist the field monitor during these visits. Continuous remote monitoring of each site's data may be performed by a centralized Novartis CRA organization. Additionally, a central analytics organization may analyze data & identify risks & trends for site operational parameters, and provide reports to Novartis Clinical Teams to assist with trial oversight.

The investigator must maintain source documents for each patient in the study, consisting of case and visit notes (hospital or clinic medical records) containing demographic and medical information, laboratory data, electrocardiograms, and the results of any other tests or assessments. All information on CRFs must be traceable to these source documents in the patient's file. The investigator must also keep the original informed consent form signed by the patient (a signed copy is given to the patient). The investigator must give the monitor access to all relevant source documents to confirm their consistency with the data capture and/or data entry. Novartis monitoring standards require full verification for the presence of informed consent, adherence to the inclusion/exclusion criteria, documentation of SAEs, and of data that will be used for all primary variables. Additional checks of the consistency of the source data with the CRFs are performed according to the study-specific monitoring plan. No information in source documents about the identity of the patients/subjects will be disclosed.

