#### **10.2** Informed consent procedures

Eligible patients/subjects may only be included in the study after providing (witnessed, where required by law or regulation), IRB/IEC-approved informed consent, or, if applicable after such consent has been provided by a legally acceptable representative(s) of the patient. Informed consent must be obtained before conducting any study-specific procedures (eg all of the procedures described in the protocol). The process of obtaining informed consent must be documented in the patient.

For trials using an Electronic Informed Consent system where a date/timestamp is automatically generated, the system-generated date/timestamp is sufficient; additional input of the date at the time of consent is not required by the patient.

Novartis will provide to investigators in a separate document a proposed informed consent form that complies with the ICH GCP guideline and regulatory requirements and is considered appropriate for this study. Any changes to the proposed consent form suggested by the investigator must be agreed to by Novartis before submission to the IRB/IEC, and a copy of the approved version must be provided to the Novartis monitor after IRB/IEC approval.

Women of child bearing potential must be informed that taking the study treatment may involve unknown risks to the fetus if pregnancy were to occur during the study and agree that in order to participate in the study they must adhere to the contraception requirement for the duration of the study. If there is any question that the patient will not reliably comply, they must not be entered in the study.

The study includes an optional DNA component which requires a separate signature if the patient agrees to participate If optional DNA collection for the study is approved by the site IRB/IEC board. It is required as part of this protocol that the Investigator presents this option to the patient. The process for obtaining consent should be exactly the same as described above for the main informed consent.

Declining to participate in these DNA assessments will in no way affect the patient's ability to participate in the main research study.

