2.1.3.2 Safety endpoints

Subject Incidence

The subject incidence for a given event in a given period is defined as the number of subjects with at least one reported occurrence of the event divided by the number of subjects who entered that period. For subjects with multiple occurrences of the same event, the event will only be counted once per subject.

Exposure-Adjusted Subject Incidence Rate

The exposure- adjusted subject incidence rate for a given event in a given period is defined as the number of subjects with at least one reported occurrence of the event in a given time period divided by total subject years at risk in that period. The time at risk for each subject will differ for each adverse event. For subjects with events, only the time until the first event contributes to the total subject years at risk. For subjects who do not experience the event, the time at risk will be calculated based on the safety analysis study window (Table 2-2). This rate will be presented per 100 subject years. For subjects with multiple occurrences of the same event, the event will be only counted once per subject.

Treatment-Emergent Adverse Event (TEAE)

Adverse Events (AEs) recorded on the Adverse Events eCRF page that occurs on or after first dose of investigational product and up to and including 112 days after the end of IP (16 weeks after the last dose of IP).

Serious Adverse Event (SAE)

SAEs determined by the flag indicating if the adverse event is serious on the Adverse Events eCRF page will include those that occur after signing of the informed consent and up to and including end of study.

Treatment-Emergent Serious Adverse Event

A treatment-emergent serious adverse event is an SAE considered to be treatment-emergent.

Treatment-Related Adverse Event

A treatment-related AE is defined as a treatment-emergent adverse event that is considered by investigators to have reasonable possibility that it may have been caused by IP as determined by the flag indicating that there is a reasonable possibility that the AE is related to investigational product on the Adverse Events eCRF page.

Treatment-Related Serious Adverse Event

A treatment-related serious adverse event is an SAE considered to be treatment-related.

Columbia-Suicide Severity Rating Scale (C-SSRS)

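### Exclusion criterion 21 ties contraception to dosing, so the eligibility list stops 12 to 16 weeks short of the Week 24 visit to which Section 10.2 requires it; planned pregnancy is excluded in Section 3.6 but not in criterion 20.

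*Protocol*

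**What the plan says.** **Eligibility list (Protocol 4.2).** Criterion 21 excludes women of child-bearing potential "unless they are using basic methods of contraception during dosing of investigational drug". It lists acceptable methods, some with a lead-in before the first dose, but gives no period after the last one. Criterion 20 covers pregnancy and breastfeeding, not an intention to conceive.

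**Consent (Protocol 10.2).** Women of child-bearing potential must agree that "they must adhere to the contraception requirement for the duration of the study". The section adds: "If there is any question that the patient will not reliably comply, they must not be entered in the study".

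**Risk section (Protocol 3.6).** Among those ruled out are women "planning to become pregnant are excluded from study participation, as well as patients who are unwilling to comply with the protocol-specified contraception requirements". The reason given is that endogenous CGRP may matter for the fetus and placenta and for vascular adaptation in pregnancy.

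**Where the list is used.** Under Protocol 5.3 the site contacts the randomization system "after confirming that the patient fulfills all the inclusion/exclusion criteria". Under Protocol 8.1 the monitoring standards "require full verification for the presence of informed consent, adherence to the inclusion/exclusion criteria", among other items.

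**The concern.** The protocol states its contraception condition in three places, and the place that works as the entry checklist has the shortest period. Take a woman who will use contraception through her last injection and then try to conceive. She is neither pregnant nor nursing, so criterion 20 does not catch her. She uses contraception while being dosed, so criterion 21 does not catch her. Only Sections 3.6 and 10.2 keep her out.

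Criterion 25 makes this harder for a site. It closes by telling investigators to add no exclusions of their own. Its general clause on compliance with study procedures might be stretched to contraception, but its example is diary completion and it names no period.

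What is at stake is patient safety during follow-up. A pregnancy requires study treatment to stop (Protocol 5.6.2), but after Week 8 no dose is left to withhold. Pregnancy testing and 24-hour reporting detect a pregnancy; they do not prevent one.

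**Working it through.** No sample-size or error-rate formula applies. The check is timeline arithmetic and a comparison of the texts.

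**Inputs**
- Doses at Day 1, Week 4 and Week 8, each within 5 days either side (Protocol 5.5.4). The last planned dose is nominally Day 56.
- End of Treatment at Week 12, Day 84 (Protocol 3.1, Table 6-1).
- Final visit at Week 24, Day 168 (Protocol 3.1, Table 6-1). A patient completes the study at the last planned visit (Protocol 5.6.1).

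**Step 1: reproduce the plan's own figure.** Table 6-1, footnote 9, puts the end of follow-up 16 weeks after the last dose. Day 168 − Day 56 = 112 days, and 112 / 7 = 16 weeks. The SAP (2.1.3.2) uses the same span when it counts adverse events as treatment-emergent "up to and including 112 days after the end of IP".

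**Step 2: shortfall of criterion 21 after dosing.** The size depends on when dosing is taken to end.

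| Reading of dosing | Criterion 21 ends | Gap to Day 168 | Weeks | Share of the 24 weeks after Day 1 |
|---|---|---|---|---|
| Ends with the last injection | Day 56 | 168 − 56 = 112 days | 16 | 16/24 = 67% |
| Runs to End of Treatment | Day 84 | 168 − 84 = 84 days | 12 | 12/24 = 50% |

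The SAP's exposure rule (2.1.1.3) counts through 27 days after the last dose. That is Day 56 + 27 = Day 83, which leaves 168 − 83 = 85 days, or about 12 weeks, so it supports the lower figure.

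**Step 3: dosing window.** With the last injection 5 days late or early and the final visit held at Day 168, the first-row gap becomes (168 − 61)/7 = 15.3 to (168 − 51)/7 = 16.7 weeks.

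**Step 4: texts side by side.**

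| Condition | Section 4.2 | Elsewhere in the protocol |
|---|---|---|
| Contraception period | During dosing (criterion 21) | Duration of the study (10.2) |
| Planning pregnancy | Not listed (criterion 20 covers pregnancy and nursing) | Excluded (3.6) |
| Doubtful compliance with contraception | Not named (criterion 25 is general) | Do not enter (10.2); excluded if unwilling (3.6) |

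Nothing else in Section 4.2 supplies the full period or the planned-pregnancy exclusion.

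**The case against.** The strongest reply is that Section 10.2 is itself an entry rule. It applies at consent, before any study procedure, and bars women whose compliance is in doubt. Section 3.6 rules out the same women separately. Both are protocol text, so the ban on investigators adding exclusions does not override them. Monitors must fully verify that consent is present, and they also check adherence to the protocol as a whole. Pregnancy tests are scheduled at Weeks 4, 8, 12 and 24. The consent form, a separate document not seen here, may already state the full period.

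Most of this stands. It means the protocol, read as a whole, does not permit stopping contraception after Week 8. A reader might infer from criterion 21 that it does, or that the two sections flatly contradict each other. Neither follows: the list is looser than a rule that still binds. What remains is that the item-by-item check is made against the looser text, and that no pregnancy test is scheduled between Weeks 12 and 24.

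A second reply is that adverse-event and treatment-emergent windows are reporting conventions and do not define fetal risk. That also stands. A reader might infer that 16 weeks of contraception is medically required. The documents give no half-life or washout and so cannot show this. Criterion 22 uses five half-lives or return of the pharmacodynamic effect to baseline for other investigational drugs. This shows only that the protocol recognizes effects can outlast dosing.

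A reader might also add the six screening and baseline weeks to the shortfall. The safety argument does not support that: no study drug is given then, pregnancy is tested at screening, baseline and Day 1, and several methods in criterion 21 already carry their own lead-in.

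**Conclusion.** The point holds as a mismatch within the protocol. After dosing, criterion 21 is 12 weeks (dosing read as treatment to Week 12) to 16 weeks (dosing read as ending with the Week 8 injection) shorter than Section 10.2 requires, and criterion 20 omits the planned-pregnancy exclusion stated in Section 3.6. The correction should be made, because the shorter text is the one confirmed at randomization and the protocol itself gives a fetal-risk reason for the requirement.

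The conclusion rests on two assumptions: that the duration of the study runs to the Week 24 visit, as Protocol 5.6.1 indicates, and that Section 10.2 states the intended period. The practical effect may be small, since consent should catch most cases. The documents allow no count of affected women. There is no bearing on the efficacy analysis, type I error, power or sample size.

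**What to change.** Three changes:

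1. Amend criterion 21 to require contraception *during dosing and through the Week 24 follow-up visit (16 weeks after the last planned dose)*.
2. Add *or planning to become pregnant during the study* to criterion 20, to match Section 3.6.
3. Check that the consent form states the same period.

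The wording should not impose a new pre-dose period, because the safety argument concerns the weeks after dosing. A start at consent could exclude a woman who begins a barrier method before Day 1 and satisfies the present criterion. If the sponsor did intend contraception during dosing only, Section 10.2 should be corrected instead, with a reason given. Either way the sections should agree.

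The cost is two short wording changes in a protocol amendment and one document check. The small downside is a longer commitment stated in the eligibility text, which Section 10.2 already imposes.
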